6.12.4. Clinical Laboratory Evaluation

The data from safety laboratory measures will be summarized at Week 16 where the lab test is planned to be collected. Postbaseline and change from baseline to postbaseline for laboratory tests will be summarized for patients who have both baseline and at least 1 post-baseline result and compared between treatment groups by using ANCOVA model with the term of treatment and baseline value of the response variable. Analyses will be provided in both SI and CN units.

The last nonmissing observation at or prior to Week 16 (planned tests including early termination) will also be analyzed by an ANCOVA model with the term of treatment, baseline value of the response variable.

The percentages of patients with treatment-emergent abnormal, high, or low laboratory results at any time during the treatment period (0 to 16 weeks) will be summarized for patients who have both baseline and at least 1 post-baseline result and compared between treatment groups using Fisher's exact tests. A treatment-emergent abnormal result is defined as a change from normal at all baseline visits to abnormal at any time during the treatment period. A treatment-emergent high result is defined as a change from a value less than or equal to the high limit at all baseline visits to a value greater than the high limit at any time during the treatment period. A treatment-emergent low result is defined as a change from a value greater than or equal to the low limit at all baseline visits to a value less than the low limit at any time during the treatment period.

Planned and unplanned measurements will be included. Covance reference ranges will generally be used to define the low and high limits. Only patients who have normal baseline values for the analysis being performed will be included in the analysis for treatment-emergence.

Liver enzymes measures will not be included in the above analyses as different analyses will be used as described in Section 6.12.3.4.2 and Section 6.12.3.4.3.

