8.1.1. Permanent Discontinuation from Study Treatment

Patients will be discontinued from the IP in the following circumstances:

- The investigator may decide that the patient should stop IP. If this decision is made because of an AE, SAE, or a clinically significant laboratory value, the study drug is discontinued for that patient and appropriate measures are to be taken. Lilly or its designee is to be alerted immediately.
- The patient may decide to stop IP.
- If the patient becomes pregnant.
- If an investigator, study site personnel performing assessments, or patient is unblinded, the patient must discontinue IP.
- If the patient, for any reason, requires treatment with another therapeutic regimen or therapeutic agent that has been demonstrated to be effective for treatment of the study indication. Discontinuation from IP should occur prior to introduction of the new agent.
- Use of prohibited concomitant medication (Guidance on restrictions for concomitant therapies is provided in Section [7.7](#)).
- Use of pump that is not allowed.
- If the patient has not used IP for more than 14 days total.
- If the patient experiences a second episode of severe hypoglycemia

Discontinuation due to a hepatic event or liver test abnormality. Patients who are discontinued from IP due to a hepatic event or liver test abnormality should have additional hepatic safety data collected via case report form (CRF).

Discontinuation of the IP for abnormal liver tests **should be considered** by the investigator when a patient meets one of the following conditions after consultation with the Lilly designated medical monitor.

- ALT or AST >8X ULN
- ALT or AST >5X ULN for more than 2 weeks
- ALT or AST >3X ULN and TBL >2X ULN or prothrombin time >1.5X ULN
- ALT or AST >3X ULN with the appearance of fatigue, nausea, vomiting, right upper-quadrant pain or tenderness, fever, rash, and/or eosinophilia (>5%)
- alkaline phosphatase (ALP) >3X ULN
- ALP >2.5X ULN and TBL >2X ULN
- ALP >2.5 ULN with the appearance of fatigue, nausea, vomiting, right quadrant pain or tenderness, fever, rash, and/or eosinophilia (>5%)

Patients discontinuing from the IP prematurely for any reason should complete AE and other follow-up procedures per Section 2 (Schedule of Activities [Table ITRO.1](#).), Section 9.2 (Adverse Events), and Section 9.4 (Safety) of this protocol.

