9.4.6.1. Hepatic Safety Monitoring

If a study patient experiences elevated ALT ≥ 3 X ULN, ALP ≥ 2 X ULN, or elevated TBL ≥ 2 X ULN, liver testing ([Appendix 4](#)) should be repeated within 3 to 5 days including ALT, AST, ALP, TBL, direct bilirubin, gamma-glutamyl transferase, and creatine kinase to confirm the abnormality and to determine if it is increasing or decreasing. If the abnormality persists or worsens, clinical and laboratory monitoring should be initiated by the investigator and in consultation with the study medical monitor. Monitoring of ALT, AST, TBL, and ALP should continue until levels normalize or return to approximate baseline levels.

Hepatic Safety Data Collection

Additional safety data should be collected via the eCRF if 1 or more of the following conditions occur:

- Elevation of serum ALT to ≥ 5 X ULN on 2 or more consecutive blood tests
- Elevation of serum TBL to ≥ 2 X ULN (except for cases of known Gilbert's syndrome)
- Elevation of serum ALP to ≥ 2 X ULN on 2 or more consecutive blood tests
- Patient discontinued from treatment due to a hepatic event or abnormality of liver tests
- Hepatic event considered to be a SAE

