6.12.3.4.2. Liver Enzyme Lab Values

The liver enzyme measures (alanine aminotransferase [ALT], aspartate aminotransferase [AST], alkaline phosphatase [ALP], direct bilirubin, total bilirubin) will be summarized by treatment group. Post-baseline value and the change from baseline (last nonmissing value before randomization) to post-baseline value at Week 16 visit (planned test) will be summarized for patients who have both a baseline and at least 1 postbaseline result, and compared between treatment groups by using ANCOVA model with the term of treatment and baseline value of the response variable. All analyses will be provided in both SI and CN units.

The last nonmissing observation at or prior to Week 26 (including early discontinuation visits) will also be analyzed by an ANCOVA model with the term of treatment, baseline value of response variable.

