6.12.3.4.3. Treatment-Emergent Elevation of Liver Enzyme Lab Values

The percentages of patients with the following elevations in hepatic laboratory tests at any time during the treatment period (0 to 16 weeks) will be summarized between treatment groups:

- The percentages of patients with post-baseline ALT measurement ≥ 3 times (3X), 5 times (5X), and 10 times (10X) the Covance upper limit of normal (ULN) will be summarized for all patients with a post-baseline value by the following baseline categories: $\leq 1X$, $> 1X$ to $< 3X$, $\geq 3X$, missing.
- The percentages of patients with post-baseline AST measurement greater than or equal to 3 3X, 5X, and 10X the Covance ULN will be summarized for all patients with a post-baseline value by the following baseline categories: $\leq 1X$, $> 1X$ to $< 3X$, $\geq 3X$, missing.
- The percentages of patients with post-baseline total bilirubin measurement ≥ 2 times (2X) the Covance ULN will be summarized for all patients with a post-baseline value by the following baseline categories: $\leq 1X$, $> 1X$ to $< 2X$, $\geq 2X$, missing.

Baseline will be the maximum observation in the baseline period including the lead-in period. The maximum value will be the maximum value from the treatment period. Planned and unplanned tests will be included.

Graphical profiles of ALT, AST, total bilirubin, and ALP will be provided for patients with an ALT or AST $\geq 3X$ ULN or total bilirubin $\geq 2X$ ULN during the treatment period. A listing for these patients will also be provided, including the actual measurement of ALT, AST, ALP, and total bilirubin, the corresponding reference high limits, demographics, disposition, drug exposure and AEs. The review for these patients includes an assessment of the proximity of any ALT or AST elevation to any total bilirubin elevation, ALP levels, other potential causes, and the temporal association with events such as nausea, vomiting, anorexia, abdominal pain, or fatigue.

All patient data, regardless of whether on IP, will be used for the above analyses related to hepatobiliary events.

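### The SAP removes ALP from the treatment-emergent laboratory analysis, but the liver sections it refers to give ALP no threshold count and no profile or listing trigger

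*SAP*

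**What the plan says.** SAP 6.12.3.4.2 lists the liver measures as ALT, AST and "alkaline phosphatase [ALP], direct bilirubin, total bilirubin) will be summarized by treatment group". It plans a Week 16 value and change from baseline, compared by ANCOVA, and a second ANCOVA on "The last nonmissing observation at or prior to Week 26 (including early discontinuation visits".

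SAP 6.12.3.4.3 has three percentage tables: ALT and AST at 3X, 5X and 10X ULN, and total bilirubin at 2X ULN. Each is split by baseline category and includes unplanned tests. The section continues: "Graphical profiles of ALT, AST, total bilirubin, and ALP will be provided for patients with an ALT or AST" of at least 3X ULN or total bilirubin of at least 2X ULN. The listing covers the same patients.

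SAP 6.12.4 defines the treatment-emergent abnormal, high and low analyses for laboratory tests in general, then states: "Liver enzymes measures will not be included in the above analyses as different analyses will be used", referring to the two liver sections.

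In Protocol 8.1.1, "Discontinuation of the IP for abnormal liver tests should be considered by the investigator" under several conditions. One is "alkaline phosphatase (ALP) >3X ULN", with nothing else attached. Another is "ALP >2.5 ULN with the appearance of fatigue, nausea, vomiting, right quadrant pain or tenderness" or certain other signs. Protocol 9.4.6.1 asks for repeat testing at ALP >=2X ULN. Its criteria for extra hepatic data include "Elevation of serum ALP to" at least 2X ULN on two or more consecutive tests.

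**The concern.** The exclusion in 6.12.4 is reasonable only if the liver sections supply a categorical analysis in exchange. They do so for ALT, AST and total bilirubin but not for ALP. Without the exclusion, the default rule would have counted ALP among the treatment-emergent high results. As written, ALP loses that count and receives nothing categorical in its place.

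ALP is the marker on which a cholestatic pattern would show without a transaminase rise, and the protocol treats it as a signal in its own right. The report would therefore have no prespecified comparison between arms of how many patients crossed the ALP levels on which the protocol acts.

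The Week 26 reference is a second, smaller problem in the same section, because no scheduled assessment occurs that late.

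**Working it through.** There is no plan figure to reproduce. The check compares rules across the two documents.

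**1. Stop-consideration rules (Protocol 8.1.1) against the SAP trigger.** The trigger in SAP 6.12.3.4.3 is ALT or AST >=3X ULN, or total bilirubin >=2X ULN. Six of the seven protocol rules were run over a grid of 13 multiples of ULN (0.5 to 10) for each of ALT, AST, ALP and total bilirubin, with and without symptoms. Prothrombin time was not varied.

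| Protocol rule | Grid points meeting it | Missed by SAP trigger |
|---|---|---|
| ALT or AST >8X | 16,224 | 0 |
| ALT or AST >3X with bilirubin >2X | 18,304 | 0 |
| ALT or AST >3X with symptoms | 14,872 | 0 |
| ALP >2.5X with bilirubin >2X | 18,928 | 0 |
| ALP >3X alone | 17,576 | 2,048 |
| ALP >2.5X with symptoms | 15,379 | 1,792 |

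The ALP-alone row can be checked by hand. Four grid values exceed 3X, so 4 x 13 x 13 x 13 x 2 = 17,576 points meet the rule. It is missed when ALT and AST are each below 3X (8 values each) and bilirubin is below 2X (4 values): 4 x 8 x 8 x 4 x 2 = 2,048.

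The counts describe the grid and are not probabilities. What matters is zero or not zero. The seventh rule (ALT or AST >5X for more than two weeks) implies ALT or AST >=3X and is caught by logic. I read the prothrombin-time alternative as also requiring ALT or AST >3X, so it is caught too. Only the two rules that ALP can meet without a transaminase or bilirubin rise are missed.

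**2. Retest rules (Protocol 9.4.6.1).** These are ALT >=3X, ALP >=2X or total bilirubin >=2X ULN. The SAP trigger reproduces the first and third, adds AST, and omits the second.

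**3. What remains for ALP.** Take ALP 3.5X ULN in one patient who would otherwise be at 1X, in an arm of 420/2 = 210. The arm mean moves by (3.5 - 1)/210 = 0.012X ULN, so the ANCOVA would not reveal it. SAP 6.1 also reports minimum and maximum, so a planned Week 16 value of that size could appear as the arm's maximum. That gives no count by threshold and no patient identity, and the Week 16 summary uses the planned test only.

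**4. Week 26.** Treatment of 16 weeks plus follow-up of 4 weeks ends at Week 20. Table ITRO 6.2 limits the last-observation chemistry analysis to planned Visits 5 to 13, including early discontinuation visits. SAP 6.12.4 uses Week 16 with planned tests.

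**The case against.** The strongest case on the other side has five parts.

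- **ALP is not dropped.** This stands. Its Week 16 value and change are analysed, with minimum and maximum. A reader might infer that a large isolated rise would be invisible, or that the trial cannot report ALP. Neither follows: the data are collected, and SAP 6.1 allows additional exploratory analyses. What is absent is a prespecified count and a way to identify the patients.
- **Other outputs may show the patient.** These include the hepatic and cholestasis adverse event searches in SAP 6.12.3.4.1, the listing of discontinuation reasons and the narratives. This stands in part. Protocol 9.4.5 calls for an adverse event only when a clinically significant finding results in a diagnosis, and stopping is only to be considered, so none of these routes is assured.
- **Table ITRO 6.2 lists a categorical chemistry analysis.** It does, for chemistry in general. The specific exclusion in 6.12.4 removes ALP. If that was not intended, the two places conflict and still need correction.
- **Few patients could be stopped on an ALP result.** Table ITRO 6.2 places the planned post-baseline chemistry analysis at Visit 13 or early discontinuation, when study insulin ends. This limits the practical reach of the stop-consideration rule. It does not remove the value of comparing arms on ALP rises, including those found on unplanned tests.
- **Week 26 looks like a drafting slip.** Agreed. A reader might infer that later off-drug retests would replace elevated values and hide the worst cases. The documents do not support that: Table ITRO 6.2 restricts the analysis to planned visits through Visit 13, the planned Week 16 analysis remains, and ALT, AST and total bilirubin keep their maximum-value tables.

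**Conclusion.** The point holds as a gap in prespecified safety reporting. Under the SAP as written, an isolated ALP rise at any of the protocol's own levels enters no laboratory categorical table, profile or listing. Two of the seven stop-consideration rules, and one of the three retest rules, have no matching SAP output.

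This rests on two readings: that the exclusion in 6.12.4 prevails over the general row in Table ITRO 6.2, and that ALP belongs to the liver measures because 6.12.3.4.2 names it there.

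A reader might extend the point with equal force to direct bilirubin. It shares the missing categorical analysis, but the protocol sets no action level for it, so there is no mismatch between protocol and SAP and it is secondary. Nor does the protocol require every monitoring threshold to become a between-arm table. The case rests on the unfulfilled referral in 6.12.4 together with the protocol's separate treatment of ALP.

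The primary and multiplicity-adjusted conclusions are unaffected. Week 26 is an internal inconsistency of limited effect.

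**What to change.** - In SAP 6.12.3.4.3, add the percentage of patients with post-baseline ALP >=2X and >3X ULN, from planned and unplanned tests. Split by baseline category as already done for total bilirubin (<=1X, >1X to <2X, >=2X, missing). The >=2X row also contains every patient above 2.5X.
- In the same section, add ALP >=2X ULN to the trigger for profiles and listing.
- At minimum, if those rows are not added, keep ALP in the treatment-emergent high analysis of 6.12.4. That would catch rises from a normal baseline, though without grading them by threshold. Direct bilirubin may be kept there as well.
- In 6.12.3.4.2, replace Week 26 with Week 16, planned tests including early discontinuation, to agree with Table ITRO 6.2 and 6.12.4.

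The ALP levels are those already in the protocol; no clinical rule changes. The cost is a few lines of SAP text and a few table rows from data already collected.

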6.12.5. Vital Signs and Other Physical Findings

Post-baseline measurements and change from baseline to post-baseline for vital signs and physical characteristics (systolic blood pressure [SBP], diastolic blood pressure [DBP], pulse rate, weight, BMI) at the scheduled visits will be summarized for patients who have both baseline and at least 1 post-baseline result.

The measurements during the treatment period (0 to 16 weeks) will be analyzed by an MMRM model with treatment, baseline value of the response variable, visit, and visit by treatment interaction as fixed factors and patient as the random factor.

An ANCOVA model will also be used for the analysis of the last nonmissing observation (including early discontinuation visit) during the treatment period and during the entire study (up to Visit 801). The ANCOVA models are the same as those used for clinical laboratory measures.

The percentages of patients with treatment-emergent high or low vital signs and weight at any time during the treatment period (0 to 16 weeks) or during the entire study including safety

follow-up period will be summarized by treatment group for patients who have both baseline and at least 1 postbaseline measurement. A treatment-emergent high result is defined as a change from a value less than or equal to the high limit at all baseline visits to a value greater than the high limit at any time that meets the specified change criteria during the treatment period or during the entire study including safety follow-up period. A treatment-emergent low result is defined as a change from a value greater than or equal to the low limit at all baseline visits to a value less than the low limit at any time that meets the specified change criteria during the treatment period or during the entire study including safety follow-up period. Treatment comparison will be based on Fisher's exact test. [Table ITRO 6.4](#) will be used to define the low and high limits and change thresholds.

Table ITRO 6.4. Categorical Criteria for Abnormal Treatment-Emergent Blood Pressure and Pulse Measurement, and Categorical Criteria for Weight for Adults

Parameter	Low	High
Systolic BP (mm Hg) (Supine or sitting – forearm at heart level)	≤ 90 and decrease from baseline ≥ 20	≥ 140 and increase from baseline ≥ 20
Diastolic BP (mm Hg) (Supine or sitting – forearm at heart level)	≤ 50 and decrease from baseline ≥ 10	≥ 90 and increase from baseline ≥ 10
Pulse (bpm) (Supine or sitting)	<50 and decrease from baseline ≥ 15	>100 and increase from baseline ≥ 15
Weight (kg) (Consistent clothing and timing in relationship to meals and voiding)	(Loss) decrease $\geq 7\%$	(Gain) increase $\geq 7\%$

Abbreviations: BP = blood pressure.

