
pooled to achieve a pooled country of at least 10 patients. All analyses using country in the model will use a pooled country, unless otherwise specified. The final pooling by country and geographic region will be finalized prior to data lock.

A graphical approach for multiple comparisons (Bretz et al. 2011) will be used to strongly control the overall Type I error (2-sided alpha level of 0.05) for testing the treatment effect for the primary and multiplicity adjusted objectives.

Baseline is defined as the last nonmissing measurement at or before the randomization visit (Visit 4) unless otherwise specified.

A restricted-maximum-likelihood-based, mixed model repeated measures (MMRM) analysis will be used to analyze continuous longitudinal variables. All the longitudinal observations at each scheduled postbaseline visit will be included in the analysis. The model for the analysis of the primary efficacy endpoint of change from baseline in HbA1c will include the fixed class effects of treatment, strata (pooled country and patient's personal CGM use during the study), visit, and treatment-by-visit interaction, as well as the continuous, fixed covariate of baseline value. For analyses of variables other than HbA1c, the HbA1c stratum ($\leq 7.5\%$, $> 7.5\%$) will be included in the model. An unstructured covariance structure will be used to model the within-patient errors. Significance tests will be based on least-squares (LS) means and Type III tests. SAS PROC MIXED will be used to perform the analysis. If this analysis fails to converge, the following covariance structures will be tested in order:

- Toeplitz with heterogeneity
- Autoregressive with heterogeneity
- Compound symmetry with heterogeneous variances
- Toeplitz
- Autoregressive
- Compound symmetry without heterogeneous variances.

The first covariance structure that converges will be used. The Kenward-Roger approximation will be used to estimate denominator degrees of freedom.

An analysis of covariance (ANCOVA) will also be used to analyze continuous variables collected only at baseline and endpoint. The model will include treatment and strata (pooled country, HbA1c stratum ($\leq 7.5\%$, $> 7.5\%$), and patient's personal CGM use during the study) as fixed effects and baseline as a covariate. Unless otherwise stated, missing endpoints will be imputed using the last-observation-carried-forward (LOCF) approach, using only postbaseline data.

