20. To compare LY900014 and Humalog with respect to quality of life as measured by the EQ-5D-5L	20. Change from baseline in EQ-5D-5L UK-population-based health state index score and EQ-VAS score at Week 16.
21. To compare LY900014 and Humalog with respect to diabetes treatment satisfaction as measured by the ITSQ	21. Change from baseline in ITSQ regimen inconvenience and lifestyle flexibility domain scores at Week 16

22. To compare LY900014 and Humalog with respect to changes in body weight	22. Change in weight (kg) from baseline to Week 16
23. To compare LY900014 and Humalog with respect to the time interval until infusion set change	23. Time interval until infusion set change during the 16-week treatment period
24. To compare LY900014 and Humalog with respect to the factors affecting dosing in pumps	24. Actual and change from baseline in factors affecting dosing in pump (CR, ISF, AIT, and frequency of use of non-normal bolus type [Square Wave or Dual Wave]), during the 16-week treatment period
25. To compare LY900014 and Humalog with respect to the proportion of patients achieving improvement from baseline in HbA1c targets	25. The proportions of patients with shifts in HbA1c to <8% and ≤9%, from baseline to Week 16
26. To compare LY900014 and Humalog with respect to glycemic variability	26. Within-day and between-day glycemic variability measured by the standard deviation and the coefficient of variation of 10-point SMBG profiles
27. To compare LY900014 and Humalog with respect to the incremental AUCs after all meals, obtained from CGM use	27. Incremental $AUC_{0-1\text{ hour}}$ and incremental $AUC_{0-2\text{ hour}}$ after all meals from each 14-day CGM session at Week 16
28. To compare LY900014 and Humalog with respect to the glucose profiles, obtained from CGM use	28. Average glucose for a 24-hour period from each 14-day CGM session at Week 16
29. To compare LY900014 and Humalog with respect to the glucose variability, obtained from CGM use	29. Interquartile range, CV, LBGI, and HBGI from each 14-day CGM session at Week 16

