5.2. Determination of Sample Size

Approximately 420 patients will be randomized in order that approximately 368 patients complete the study through the primary endpoint at Week 16.

[figure not shown]
The primary objective of this study is to test the hypothesis that LY900014 is noninferior to Humalog on glycemic control as measured by change from baseline to Week 16 in HbA1c in patients with T1D when administered in a double-blind manner using CSII with bolus doses delivered 0 to 2 minutes prior to the meal.

Patients will be randomized in a 1:1 ratio to double-blind LY900014 with bolus dose delivered 0 to 2 minutes before meals or double-blind Humalog with bolus doses delivered 0 to 2 minutes before meals. Assuming a noninferiority margin (NIM) of 0.4%, no true difference between treatment groups, and a standard deviation (SD) of 0.88%, 368 completers (184 in each treatment group) will provide at least 99% power to show noninferiority between LY900014 and Humalog in change from baseline to Week 16 in HbA1c using the upper limit of a two-sided 95% confidence interval (CI) (LY900014 – Humalog). Assuming a 12% dropout rate for 16 weeks, approximately 420 patients will need to be randomized. This sample size also has 90% power to show noninferiority between LY900014 and Humalog using a 0.3% NIM at Week 16.

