6.1. General Considerations

Statistical analysis of this study will be the responsibility of Eli Lilly and Company (hereafter Lilly) or its designee. Any change to the data analysis methods described in the protocol will require an amendment ONLY if it changes a principal feature of the protocol. Any other change to the data analysis methods described in the protocol, and the justification for making the change, will be described in the SAP or the clinical study report (CSR). Additional exploratory analyses of data will be conducted, as deemed appropriate.

For purposes of analysis, the following populations are defined in [Table ITRO 6.1](#).

Table ITRO 6.1. Patient Populations

Population	Description
Entered	All patients who give informed consent.
Enrolled	All patients who receive at least 1 dose of open-label Humalog in the 2-week lead-in period.
Randomized	All patients who are randomly assigned to study treatment at Visit 4. Treatment group will be defined based on the treatment the patients are assigned.
Safety	All randomized patients who receive at least 1 dose of the randomly assigned IP. Treatment group will be defined based on the treatment the patients were assigned.

Abbreviations: IP = investigational product.

Unless otherwise stated, the efficacy analyses will be conducted on the Randomized Population and the safety analyses will be conducted on the Safety Population.

The primary analysis is for the treatment period up through Week 16.

Unless otherwise noted, all tests of treatment effects will be conducted at a 2-sided alpha level of 0.05, and CIs will be calculated at 95%, 2-sided. All tests of interactions between treatment groups and other factors will be conducted at a 2-sided alpha level of 0.10.

The definitions of baseline and post-baseline for the efficacy and safety analyses depend on which analysis period is being used. The following analysis periods will be used:

- Lead-in Period – Visits 2 to 4
- 16-Week Treatment Period – from randomization to Week 16 prior to discontinuation of IP and from randomization to Week 16 (including all data regardless of IP use)
- 16-Week Treatment Period and Safety Follow-Up Visit – from randomization to Visit 801 (including all data regardless of IP use)

The data on IP is defined based on the following rules:

- For data only measured at an office visit
 - MMTT postbaseline data will be classified as on IP if the MMTT performance date is prior to or on the last IP dose date

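### The weight and vital-sign MMRM in SAP 6.12.5 departs without a stated reason from the protocol's unstructured covariance; read literally, its Week 16 standard error is wrong if variance changes over visits

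*SAP*

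**What the plan says.** - **SAP 6.12.5** covers blood pressure, pulse rate, weight and BMI. Measurements over Weeks 0 to 16 go into an MMRM with treatment, baseline value, "visit, and visit by treatment interaction as fixed factors and patient as the random factor". No covariance, fallback list or degrees-of-freedom method follows. The section also plans an ANCOVA of the last nonmissing observation and Fisher's exact test on categorical changes. For weight, Table ITRO 6.4 sets the category at a gain or loss of at least 7%.
- **Protocol 10.3.1** defines the MMRM for continuous longitudinal variables: "An unstructured covariance structure will be used to model the within-patient errors". Six alternatives are tried in order if that fails to converge, and homogeneous compound symmetry is the last. Degrees of freedom are Kenward-Roger.
- **Protocol 10.3.3.3** refers continuous tertiary and exploratory variables to the models of 10.3.1 and leaves further detail to the SAP. Weight is tertiary objective 22: "Change in weight (kg) from baseline to Week 16".
- **Protocol 10.3.4** says only that continuous safety variables are analysed by MMRM or ANCOVA.
- **Protocol 10.3.1 and SAP 6.1** allow non-principal changes of method, but ask that the SAP or study report give the justification.

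**The concern.** A random patient effect with independent, equal-variance residuals implies the same variance at every visit and the same correlation between every pair of visits. That is homogeneous compound symmetry, the structure the protocol accepts only after all the others have failed.

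Under such a model the standard error of the Week 16 difference comes from a variance pooled over all post-baseline visits. If weight change spreads out over 16 weeks of titration, early visits pull the pooled variance below the Week 16 value. The Week 16 confidence interval is then too narrow and its p-value too small, while early-visit intervals are too wide. Weight change is a safety comparison of interest for an insulin, and SAP 6.1 has intervals and p-values displayed for continuous measures.

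**Working it through.** **The plan's own figures.** Neither document states an SD, power or error rate for weight or vital signs. The sample-size statement concerns HbA1c only: "368 completers (184 in each treatment group) will provide at least 99% power to show noninferiority". With SD 0.88%, SE = 0.88 × sqrt(2/184) = 0.0917. Power is Φ(0.4/0.0917 − 1.96) = 99.2% at the 0.4% margin and Φ(0.3/0.0917 − 1.96) = 90.5% at 0.3%. Also 368/(1 − 0.12) = 418.2, rounded up to 419. All agree with the plan, but none says how weight varies over visits.

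**Inputs for the check.** From SAP 6.1: "all tests of treatment effects will be conducted at a 2-sided alpha level of 0.05". From SAP 5.2: 1:1 allocation, about 420 randomized, 12% dropout. By assumption: the SD of weight change at each visit, and three or four post-baseline weight visits, because the schedule table does not read cleanly in the copy available.

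**Formula.** With complete data, the random-intercept model estimates the Week 16 difference by the baseline-adjusted difference in Week 16 means. Its standard error uses the mean of the visit variances. Hence

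true type I error = 2 × [1 − Φ(1.96 × sqrt(mean visit variance / Week 16 variance))].

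**Worked case.** For SDs 2.0, 2.25 and 2.5 kg the variances are 4, 5.0625 and 6.25, with mean 5.104. The ratio is 5.104/6.25 = 0.817 and its square root 0.904. Then 1.96 × 0.904 = 1.771, and 2 × [1 − Φ(1.771)] = 7.7%.

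**Simulation check.** REML random-intercept fit, 210 per arm, 12% random monotone dropout, 2000 runs per scenario, no true difference, cutoff 1.96.

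| Assumed pattern of weight change | Formula | Simulated |
|---|---|---|
| Constant variance | 5.0% | 5.9% |
| SDs 2.2 / 2.35 / 2.5 kg | 6.5% | not run |
| SDs 2.0 / 2.25 / 2.5 kg | 7.7% | 8.4% |
| SDs 1.8 / 2.1 / 2.5 kg | 9.1% | 9.6% |
| SDs 1.5 / 2.0 / 2.5 kg | 11.0% | not run |
| SDs 1.3 / 1.8 / 2.5 kg | 13.0% | 14.2% |
| Random walk, Weeks 4, 8, 16 | 13.4% | 13.2% |
| Random walk, Weeks 2, 6, 14, 16 | 13.1% | 14.7% |
| Random walk, Weeks 2, 4, 8, 16 | 18.0% | 20.6% |
| Falling SDs 2.5 / 2.4 / 2.3 kg | 4.1% | 4.3% |

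The simulation standard error is about 0.5 percentage points at a true 5%: sqrt(0.05 × 0.95/2000) = 0.0049.

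**What a given rate requires.** Setting the formula to 10%, the Week 16 variance must be (1.960/1.645)² = 1.42 times the mean over visits. For 20% it must be (1.960/1.282)² = 2.34 times.

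**After the fix.** A Week 16 ANCOVA on observed cases, used as a stand-in for the unstructured model because it takes only the Week 16 variance, rejected in 4.3% to 5.5% of runs across the simulated scenarios.

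**The case against.** The strongest reply is that the SAP never says compound symmetry or equal variance. It calls the model an MMRM, which the protocol defines with unstructured errors. Naming patient as random may be loose wording for patient as the repeated-measures subject. Near-identical wording for the antibody model in SAP 6.12.7.1 suggests a stock sentence. A random intercept can also be combined with visit-specific residual variances. This stands in part: a reader might infer that the SAP prescribes equal variance at every visit, but that is the literal reading of an incomplete specification, not a stated choice. Against the reply, SAP 6.11.1 spells out the unstructured model, and SAP 6.12.6.1 and 6.13 refer back to the primary-endpoint model. SAP 6.12.5 does neither, so a programmer following it as written would fit a random intercept.

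A reader might also infer that the weight test rejects a true null 10% to 20% of the time. The documents do not support that. They give no weight SDs by visit, and modest growth gives less than 10%.

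The protocol departure is softer than it may first look, because Protocol 10.3.4 names no covariance for safety variables. But Protocol 10.3.3.3 does point weight, as a tertiary endpoint, to 10.3.1, and the SAP gives no justification for differing.

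Finally, a misleading MMRM p-value for weight would not stand alone. The last-observation ANCOVA does not pool variance over visits, and the categorical test is separate. This stands and lowers the stakes. The ANCOVA is not a full substitute, since dropouts contribute earlier values while objective 22 is at Week 16.

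**Conclusion.** The point holds as a low-severity specification defect. SAP 6.12.5 leaves open, or read literally replaces, the covariance that Protocol 10.3.1 sets, and gives no reason.

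On the literal reading, the Week 16 standard error is wrong whenever variance changes over visits. Conditional on the assumed pattern, type I error at nominal 5% is:

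- 5% with constant variance;
- about 6-10% with modest growth;
- about 11-15% with strong growth;
- near 20% only with steep growth;
- slightly below 5% if variance falls.

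Coverage of the 95% interval falls or rises to match. The point estimate is essentially unaffected. Blood pressure and pulse are probably little affected, on the assumption that the variance of their change is roughly flat over visits. Weight is exploratory, and SAP 6.5 makes no multiplicity adjustment outside the primary and multiplicity-adjusted objectives, so no confirmatory claim depends on this model.

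**What to change.** In SAP 6.12.5, replace the random-patient wording with the Protocol 10.3.1 rule: unstructured within-patient covariance, the same ordered fallback list, and Kenward-Roger degrees of freedom. A cross-reference to the covariance text in SAP 6.11.1 would do. Align the same wording for the antibody MMRM in SAP 6.12.7.1. If a random-intercept model is intended, say so and give the reason.

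The cost is a sentence in the SAP, a line of model code and a few more covariance parameters, which about 420 patients support easily. No extra data are needed. If the variances turn out equal, practically nothing is lost.
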